5.6.3. Considerations with the Use of OCA and Bezafibrate in Combination

As both OCA and BZF are metabolized in the liver, it is important to monitor for potential hepatotoxicity through physical signs and symptoms, as well as laboratory testing of liver-related biochemical parameters. See [Section 7.4](#) for guidance on the monitoring and management of potential hepatic events and decompensation.

In considering use of BZF and OCA concomitantly and the Phase 2 study data to date, it is expected that the safety experience will be similar to the individual products. However, the overall safety profile of BZF is based on a different patient population and indication for the treatment of severe hypertriglyceridaemia and mixed hyperlipidaemia. Decreased appetite and gastrointestinal disorders were the most common undesirable effects. Per the Summary of Product Characteristics, cholelithiasis is a labeled undesirable effect of BZF (very rare) ([Bezalip Mono 2016](#), [Bezalip Mono 2020](#), [Bezafibrate Retard 2017](#), [Bezalip 2016](#), [Bezalip 2020](#)) and has also been reported in OCA clinical studies at higher doses in subjects with metabolic dysfunction-associated steatohepatitis (MASH). [Section 7.5](#) provides detailed guidelines for the medical management of subjects with symptomatic cholelithiasis and/or cholecystitis.

Treatment with drugs of the fibrate class including BZF has been associated on rare occasions with myositis or rhabdomyolysis. Myopathy should be considered in any subject with diffuse myalgias, muscle tenderness/weakness, or marked elevations in CK levels, and dose adjustment may be needed in subjects with impaired renal function. Subjects should be advised to report unexplained muscle pain, tenderness or weakness promptly, particularly if accompanied by malaise or fever. Creatine kinase (CK) levels should be assessed in subjects reporting these symptoms, and investigational product should be interrupted if markedly elevated CK levels ($\geq 5\times$ ULN or $\geq 3\times$ ULN with symptoms of rhabdomyolysis) occur or myopathy is diagnosed (Table 4). Section 7.4.4.3 provides detailed guidelines for evaluating and monitoring subjects with potential myopathy. In cases of rhabdomyolysis, administration of investigational product must be stopped immediately and renal function must be carefully monitored while rehydration is administered.

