Notes: Unscheduled visits should occur as needed in the event of signs or symptoms of suspected hepatic injury or decompensation or if laboratory alerts have been triggered. Subjects who discontinue investigational product but continue in the study may be requested to come in for an Unscheduled Visit at the discretion of the Investigator depending on the timing of their next scheduled study visit. Unscheduled visits are optional and should occur as needed based on Investigator discretion; a PK sample should be collected if an unscheduled visit occurs due to a safety event.

^a The Day 2 Visit can be either a virtual or onsite visit. It will be scheduled on Day 2 to Day 7 of the study depending on when laboratory results are available and reviewed. Subjects can elect to pickup IP onsite (onsite Day 2 visit) or have it shipped directly to them (virtual Day 2 visit). For subjects that have IP shipped, the Day 2 virtual visit should be scheduled once the subject receives IP.

^b An ET visit should occur in subjects who withdraw from the study. The ET visit should be completed as near as possible to the subject's last dose of IP. Study procedures and assessments are not required if previously completed within 4 weeks of the ET.

^c Subjects should be instructed to fast overnight (at least 8 hours) before all in-clinic study visits, but water is permitted. Record fasting status in the source and eCRF. If the subject reports having eaten or drunk anything other than water within 8 hours, document accordingly in the source and eCRF and remind the subject that fasting is required before all onsite study visits.

^d On the Day 2 Visit, the Investigator will review Day 1 eligibility laboratory results. If any laboratory results are out of range, the Medical Monitor and Sponsor Medical Monitor will review and determine an appropriate plan for the subject on a case-by-case basis.

^e If subjects develop myopathy at any point during the study, CK values must be checked. A CK $\geq 5 \times$ ULN or $\geq 3 \times$ ULN with symptoms consistent with rhabdomyolysis will require investigational product interruption. Laboratory values including CK and creatinine will be closely monitored every 2 weeks until values return to baseline levels.

^f Waist-to-hip ratio will be calculated via EDC from waist and hip circumference measurement.

^g Body temperature, sitting heart rate, respiratory rate, and seated blood pressure after sitting for 3 minutes.

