7.4. Monitoring and Management of Potential Hepatic Injury and/or Disease Progression

Given the chronic and progressive nature of PBC, it is important to monitor for potential hepatic injury, disease progression, and/or hepatic decompensation. CP and MELD scores will be reviewed at each visit where labs are drawn ([Section 7.4.4](#) and [Section 14.2.1](#)). CP Scores should only be applied in subjects who have evidence of cirrhosis or progression to cirrhosis based on criteria presented in [Section 7.4.4](#). In addition, AEs, signs and symptoms of potential hepatic injury or decompensation, and laboratory values will also be reviewed at regular intervals as described in [Section 7.1.3](#). Based on the assessments of signs and symptoms of hepatic injury and/or muscular injury and liver biochemistry ([Section 7.4.1](#) and [Section 7.4.2](#)), the investigational product (OCA + BZF) may be interrupted or discontinued per the criteria discussed in [Section 7.4.2](#) and [Section 7.4.3](#).

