- Unscheduled visits as needed in the event of signs or symptoms of potential hepatic and/or muscular injury or decompensation or if laboratory alerts have been triggered

It is important that the laboratory assessments be completed as required and that the central laboratory be used for assessments whenever possible. In the event that a subject cannot return to the clinic for a scheduled or unscheduled visit, or there is an event that triggers a need for an immediate assessment, the use of a local lab is permissible at the discretion of the Investigator. In these cases, the Investigator will obtain the laboratory results and the laboratory normal ranges.

The process for assessing criteria is presented in Figure 2, and the specific threshold(s) for each laboratory analyte to trigger investigational product interruption are summarized in Table 5.

Figure 2: Management Algorithm for Potential Hepatic and/or Muscular Injury

CK=creatine kinase; INR=international normalized ratio; IP=Investigational Product; PK=pharmacokinetic

Notes: Laboratory assessments include: ALT, ALP, AST, GGT, direct and total bilirubin, INR, and CK.

PK sampling should be conducted within 7 days of IP interruption; close monitoring including physical exams and repeat biochemistry labs should occur as often as deemed appropriate by the Investigator (Table 4).

Table 4: Laboratory Criteria for Monitoring of Potential Hepatic and Muscular Injury for Interruption^a of Investigational Product

Baseline ^b	Treatment Emergent	Liver Signs and Symptoms ^c
Any value	Any hepatic enzyme elevation (TB, ALP, AST, ALT, GGT)	Yes
ALT or AST Normal	ALT or AST ≥ 3 x ULN and TB ≥ 2 x BL	Yes or No
	ALT or AST ≥ 3 x ULN and INR >1.5	Yes or No
	ALT or AST ≥ 5 x ULN and Any TB	Yes or No
ALT or AST Elevated	ALT or AST ≥ 2 x BL and TB ≥ 2 x BL	Yes or No
	ALT or AST ≥ 2 x BL and INR >1.5	Yes or No
	ALT or AST ≥ 3 x BL (or ≥ 300 U/L, whichever occurs first) and Any TB	Yes or No
TB \leq ULN	TB ≥ 2 x BL and $>$ ULN	Yes or No
TB $>$ ULN	TB ≥ 1.5 x BL or ≥ 3.0 mg/dL, whichever occurs first	Yes or No
ALP \leq ULN	ALP ≥ 2 x BL and $>$ ULN	Yes or No
ALP $>$ ULN	ALP ≥ 2 x BL or ≥ 1000 U/L, whichever occurs first	Yes or No
CK	≥ 5 x ULN or ≥ 3 x ULN with symptoms of rhabdomyolysis ^{d,e}	N/A

BL=baseline; CK=creatinine kinase; DILI=drug-induced liver injury; INR=international normalized ratio; IP=investigational product; N/A=not applicable; TB=total bilirubin

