^a Interrupt study drug; Initiate workup of competing etiologies and close monitoring (repeat labs and exam 2-3 times per week), including repeat labs initially.

- Study drug can be restarted after a minimum of 30 days if another etiology is identified, liver enzymes return to baseline, lab abnormalities are determined not to be due to DILI, no symptoms, and approved by the Medical Monitor and Investigator.
- If study drug is restarted after 30 days, repeat labs in 2-5 days for ALT, AST, and TB or 7-10 days for ALP as indicated and continue close monitoring.

^b New baseline values for DILI monitoring for ALT, AST, ALP, TB should be determined based upon average of Month 3 and Month 6 values if average is $>50\%$ decrease from original baseline. Adapted from [Palmer 2020](#).

^c Liver signs and symptoms to include: new onset severe fatigue or significant worsening of baseline fatigue; new onset severe pruritus or significant worsening on baseline pruritus; nausea, vomiting, right upper quadrant pain; fever, rash, or $>5\%$ eosinophilia; new onset of hepatic decompensation (e.g., ascites, variceal bleeding, hepatic encephalopathy).

^d Symptoms of rhabdomyolysis may include muscle swelling; weak, tender or sore muscles; dark urine; fever; tachycardia; nausea and vomiting; confusion; dehydration; or abdominal pain.

^e If IP interrupted due to CK trigger, closely monitor CK and creatinine/renal function in addition to liver biochemistries every 2 weeks until values return to baseline levels; same criteria apply to considering re-initiation of IP. CK levels should be assessed in patients reporting symptoms of rhabdomyolysis, and investigational product should be discontinued if markedly elevated CK levels (≥ 5 x ULN) occur or myopathy is diagnosed.

It should be noted that it is difficult to recognize every potential marker of hepatic deterioration or muscular injury. There is no substitute for good medical judgment. Investigators will be reminded to be cautious and mindful in their evaluation of subjects' symptoms, signs, and laboratory results. However, for example, a single abnormal laboratory analyte result may be artifactual; accordingly, Investigators will be allowed to implement an alternate follow-up procedure if considered appropriate based on their medical judgement but only after documented agreement with the Sponsor's Medical Monitor.

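### A Day 1 CK of at least 5×ULN is excluded by criterion 25 yet may be admitted case by case under 7.4.4.3; a lesser verb mismatch leaves unclear whether diagnosed myopathy is a final stop

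*Protocol*

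**What the plan says.** **Day 1 eligibility.** Exclusion criterion 25 appears in the protocol synopsis and in 8.3. Its first limb excludes a Day 1 CK of 5×ULN or more. The clause about the opinion of the Principal Investigator and Sponsor belongs to the second limb, on other abnormal laboratory values at the last parent-study visit, and does not soften the CK limb. Section 7.4.4.3 takes the same cut-off at Day 1/Day 2 and leaves continuation to the two medical monitors, case by case. Table 3 footnote d and 9.7.2.2 give those monitors the same discretion over any out-of-range Day 1 eligibility result. Section 9.7.2.2 also restricts dispensing to subjects who are still eligible.

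**CK and myopathy on treatment.** Section 5.6.3 says "investigational product should be interrupted if markedly elevated CK levels" occur or myopathy is diagnosed, and cites Table 4. The last sentence of Table 4 footnote e (7.4.2) has almost the same wording with another verb: "investigational product should be discontinued if markedly elevated CK levels". The Table 4 title reads "Laboratory Criteria for Monitoring of Potential Hepatic and Muscular Injury for Interruption". Table 3 footnote e and 7.4.4.3 both say that CK at the threshold, or lower "with symptoms consistent with rhabdomyolysis will require investigational product interruption". The first sentence of footnote e treats the CK trigger as an interruption and adds "same criteria apply to considering re-initiation of IP". For rhabdomyolysis, 5.6.3 says "In cases of rhabdomyolysis, administration of investigational product must be stopped immediately", without saying whether the stop is permanent.

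**The concern.** The first conflict decides whether a subject is dosed at all. One site can screen-fail a Day 1 CK of 5×ULN under criterion 25. Another can refer the same result under 7.4.4.3 and go on to dose. The second subject then receives a fibrate while meeting an exclusion criterion written for a known fibrate risk: Protocol Table 2 lists myositis and rhabdomyolysis for bezafibrate. SAP 6.1 summarises major deviations, but neither document says whether dosing on the monitors' decision is one.

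The second conflict decides what happens to a treated subject. Section 7.4 treats the two actions as different, since product "may be interrupted or discontinued per the criteria discussed in" the sections that follow. Depending on how a site reads footnote e, the same event could be recorded as a temporary discontinuation, subtracted from exposure under SAP 10.1, or as a drug withdrawal, which enters the SAP 10.2.3 table of events leading to withdrawal. In a study whose primary objective is long-term safety and tolerability, those are reported results.

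**Working it through.** No arithmetic underlies the point, and the plan states no figure to reproduce. The check is to set the current texts side by side.

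**Step 1: Day 1 CK of 5×ULN or more.**

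| Place | Rule |
|---|---|
| Synopsis, criterion 25 | Excluded, no exception |
| 8.3, criterion 25 | Excluded, no exception |
| 7.4.4.3 | Two monitors decide case by case, CK named |
| Table 3 footnote d | Two monitors set a plan case by case, any out-of-range eligibility result |
| 9.7.2.2 | As footnote d; dispense only to subjects still eligible |

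Two places exclude. One allows continuation specifically for CK, and two give a general case-by-case route. The cut-off is identical wherever CK is named, so both rules cannot govern the same subject. The Version 2.0 summary of changes records the case-by-case wording of 7.4.4.3 as a deliberate revision and lists no matching change to criterion 25. That shows where the mismatch came from; the mismatch itself lies in the current text.

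**Step 2: CK of 5×ULN or more on treatment, or diagnosed myopathy.**

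| Place | Action |
|---|---|
| 5.6.3 | Interrupt (CK threshold, or diagnosed myopathy) |
| Table 4 title and CK row | Interrupt (CK threshold) |
| Table 3 footnote e | Interrupt (CK threshold) |
| 7.4.4.3 | Interrupt (CK threshold) |
| Table 4 footnote e, first sentence | Interruption, with possible re-initiation |
| Table 4 footnote e, last sentence | Discontinue (CK threshold, or diagnosed myopathy) |

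Five places treat the CK trigger as an interruption and one says discontinue. The discontinue sentence opens with patients who report rhabdomyolysis symptoms, so it bears on symptomatic subjects with CK of at least 5×ULN and on diagnosed myopathy. From 3× to below 5×ULN with symptoms, every place that sets an action says interrupt.

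**Step 3: myopathy diagnosed below the CK thresholds.** Table 3 footnote e, the Table 4 CK row and 7.4.4.3 act only on CK values. The specific rules that remain are 5.6.3 and the last sentence of footnote e, which disagree one to one.

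**Step 4: does another section settle it?**
- 8.4.1.1 forces a stop only for adverse events that are Grade 3 or worse and related. Table 9 grades by limitation of usual activities, so milder myopathy is not covered.
- Table 5 and 8.4.1, the permanent-stop rules, do not list CK or myopathy.
- 8.4.2 accepts the development of an exclusion-criterion condition that might jeopardise safety as a reason to stop, but does not require it. Criterion 8 bars entry to anyone with a history of drug-induced myopathy.

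None of these says whether diagnosed myopathy ends treatment.

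**The case against.** **On eligibility.** The strongest reply is that the Day 2 process is coherent. Three places describe review by two monitors, nobody is admitted automatically, and the revision of 7.4.4.3 was deliberate. That stands as mitigation. It does not create an exception to criterion 25, which has none, and 9.7.2.2 itself dispenses only to subjects still eligible. A reader might infer that 7.4.4.3 alone is out of line. The documents do not support that either: Table 3 footnote d and 9.7.2.2 leave the same route open unless they are read as subordinate to the exclusion criteria, which they do not say.

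**On the verb.** A reader might infer that footnote e orders a permanent stop for every CK of at least 5×ULN, and that the protocol therefore intends two different actions. The text does not support this. The sentence is framed around symptomatic patients. Sections 7.4.3 and 8.4.1 say permanent when they mean it, SAP 10.1 speaks of temporary discontinuation, and 7.4.4.3 introduces its criteria as interruption/discontinuation together. Against that, 7.5 uses discontinuation without qualification in contrast to interruption with resumption, so a site could reasonably read it as final.

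**On harm.** A reader might also infer that sites can freely re-expose such subjects. They cannot. Footnote a says "Study drug can be restarted after a minimum of 30 days if another etiology is identified", and also requires absence of symptoms and approval by the Medical Monitor and Investigator. A CK rise attributed to the fibrate would not meet the requirement for another cause. The risk of re-exposure is therefore narrow.

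**Conclusion.** The protocol is wrong as written on eligibility: criterion 25 excludes a subject whom 7.4.4.3 may admit, at the same threshold. This should be fixed. On treatment the fault is smaller. One sentence of footnote e departs from five other places, probably through loose drafting, but the question of whether diagnosed myopathy is a final stop remains unanswered.

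The number of subjects affected cannot be estimated, because neither document gives a CK event rate. Nothing in the descriptive analysis methods changes, and a dosed subject stays in the LTSE Population either way. What is affected is who is dosed, how the event is recorded, and whether a deviation is counted.

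Two limits apply. Figure 2, the management algorithm for hepatic and muscular injury, is not shown in the text available, so whether it resolves the second point cannot be judged. A reader might also convert the multiples of ULN into U/L using the SAP 10.3 ranges. Those ranges define abnormal flags for analysis; 7.4.2 permits local laboratories with their own ranges, and nothing shows that the SAP values are the triggers used at sites.

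**What to change.** **Day 1 rule.** Make one rule govern in all places. The safer option is for 7.4.4.3 to say that a Day 1 CK of 5×ULN or more is not eligible, and for Table 3 footnote d and 9.7.2.2 to say that case-by-case review does not override exclusion criteria (three edits). If the Version 2.0 change was intended, add the two-monitor exception to criterion 25 in both the synopsis and 8.3 instead (two edits).

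**On-treatment rule.** In Table 4 footnote e, use interruption for CK of 5×ULN or more, with restart only under footnote a. State there that drug-related myopathy or rhabdomyolysis means permanent discontinuation, and match the wording in 5.6.3 (two edits). Check Figure 2 against the result.

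**Editorial only.** In 7.4.2, the pointer for the laboratory interruption thresholds should be to Table 4, not Table 5 (one edit).

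The total is 3 + 2 + 1 = 6 short edits with the safer option, or 2 + 2 + 1 = 5 with the alternative, in one amendment. The sponsor must make two clinical decisions: which Day 1 rule governs, and whether it accepts the permanent stop. No new data and no change to SAP methods are needed.

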7.4.3. Clinical Criteria for Monitoring for Potential Hepatic Decompensation Events

Subjects will be monitored for potential hepatic decompensation events throughout the study. Investigational product is to be permanently discontinued with the development of any clinical events listed in Table 5.

Subjects who experience hepatic decompensation events should be closely monitored until normalization or stabilization using good clinical judgement, and, per Food and Drug Administration (FDA) guidance for observation of potential DILI, should include, but not be limited to, a thorough clinical evaluation including repeat liver enzymes and tests of liver function two to three times weekly with subsequent frequency to be determined by clinical status; complete history and physical; evaluation of concomitant drugs, alcohol, illicit drug use; concomitant liver conditions including viral hepatitis; environmental exposures; consider gastroenterology or hepatology consultation.

After stabilization, subjects should continue with scheduled study visits for safety follow up.

Table 5: Clinical Criteria for Monitoring Potential Hepatic Decompensation Events and Mandatory Discontinuation of Investigational Product

 • Clinical evidence of portal hypertension, defined as 
 ○ Platelet count <150,000/μL ○ Splenomegaly on ultrasound ○ Non-bleeding varices on endoscopy • Evidence of hepatic decompensation 
 ○ Progression to CP score ≥7 ○ Ascites including hepatic hydrothorax ○ Hepatic encephalopathy – requiring hospitalization and/or lactulose and/or rifaximin ○ Hepatorenal syndrome (Type 1 or Type 2), hepatopulmonary syndrome, or portopulmonary syndrome ○ Variceal hemorrhage ○ Jaundice (with total bilirubin >3 mg/dL [$>51.3 \mu\text{mol/L}$]) ○ MELD ≥15 • HCC • Any liver-related event requiring hospitalization and treatment • Evaluation, listing, or completion of a liver transplant
--

CP=Child-Pugh; HCC=hepatocellular carcinoma; MELD=Model for End-stage Liver Disease

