BZF may enhance the action of anticoagulants of the coumarin type. Therefore, the dose of the anticoagulant should be reduced by 30% to 50% at the start of treatment with BZF and then titrated according to the blood clotting parameters. Since some subjects are on anticoagulants and may develop a variceal bleed, special precaution should be taken to monitor and adjust their anticoagulant doses as needed. International normalized ratio (INR) is decreased following co-administration of warfarin and OCA. INR should be monitored, and the dose of warfarin adjusted, if needed.

BZF should not be dosed at the same time as cholestyramine in those patients whose medical conditions require it. When the combination of BZF SR 400 mg tablets with OCA are administered concurrently with resins, an interval of 4 hours should be maintained between the 2 drugs.

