7.4.4.1. Criteria for Assessing Cirrhosis

Acceptable methods of confirming (via medical history) or assessing cirrhosis include documented evidence or presence of one or more of the following cirrhosis indicators:

- Biopsy results consistent with PBC Stage 4 (Ludwig 1978)
- TE Median Value ≥ 16.9 kPa (Corpechot 2012)
- The presence of any of the following in the absence of acute liver failure:
 - Varices
 - Ascites
 - Radiological evidence of cirrhosis (e.g., nodular liver or enlargement of portal vein and splenomegaly)
- Combined low platelet count ($<150,000/\mu\text{L}$) with:
 - Persistent decrease in serum albumin, or
 - Elevation in PT/INR (not due to antithrombotic agent use), or
 - Elevated bilirubin (2x ULN)

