9.2.3. Anticoagulants

Use of anticoagulants (e.g., warfarin) should be monitored and the dose adjusted, if needed. Taken concomitantly, OCA and warfarin may decrease INR, and BZF may potentiate the action of coumarin-type anticoagulants.

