14.2. Other Safety Parameters

14.2.1. MELD Score

The MELD scoring system is used to assess the severity of chronic liver disease. The MELD score is useful in assessing patients with significant decompensation and the MELD score is now used by the United Network for Organ Sharing in the US and Eurotransplants to manage the organ allocation for liver transplantation. The threshold for placement on an organ transplantation queue varies between regions across the globe, but a score of 15 may result in a place on the transplant waiting list in the US.

An increasing MELD score is associated with increased severity of hepatic dysfunction and increased 3-month mortality risk. The MELD score is derived from the patient's serum total bilirubin, serum creatinine, and INR, as appropriate, to predict survival and is calculated according to the following formula ([Kamath 2007](#)):

$$\text{MELD} = 3.78 \times \ln(\text{serum bilirubin [mg/dL]}) + 11.2 \times \ln(\text{INR}) + 9.57 \times \ln(\text{serum creatinine [mg/dL]}) + 6.43$$

INR will be calculated based on PT value by the central laboratory.

MELD score will be reported in whole numbers on the eCRF according to the frequency listed in [Table 3](#).

For a MELD score ≥ 15 to be considered as an outcome endpoint, an indication of the presence of cirrhosis and the progression of liver disease must be present. However, transient increases of total bilirubin, creatinine, or INR values due to causes other than progression of liver disease should be ruled out (e.g. use of medications that may cause an increase in INR). In addition, it should be ascertained by the adjudicators that the change in MELD score is sustained and not transient. Additionally, the subject must have MELD ≤ 12 at baseline (defined as the last assessment performed before the first dose of investigational product in Study 977-311).

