9.1. Efficacy Endpoints

The LTSE Population will be the population used for the efficacy analyses. Baseline is defined as the last assessment performed before the first dose of investigational product in Study 977-311, unless otherwise specified.

The efficacy endpoint at post-baseline site visits includes:

- Response rate of $\geq 40\%$ reduction from baseline and normalization rates of ALP
- Normalization rates of GGT, ALT, AST, total and conjugated bilirubin
- Change from baseline in GGT, ALT, ALP, AST, and total and conjugated bilirubin
- Percentage of subjects with ALP $< 1.67 \times \text{ULN}$, total bilirubin $\leq \text{ULN}$, and ALP decrease of $\geq 15\%$ from baseline
- Change from baseline in noninvasive markers of liver fibrosis, including liver stiffness measured by TE and ELF score
- Change from baseline in the GLOBE, UK-PBC, and MELD scores

All continuous and categorical additional endpoints will be summarized using descriptive statistics at baseline and at each scheduled post-baseline visit. No statistical inference will be done on those endpoints.

[figure not shown]
The intercurrent event in this study includes the use of prohibited medication and treatment discontinuation. Data collected after the intercurrent events, such as the use of prohibited medications, and data collected after treatment discontinuation will be included in the analyses (Treatment Policy Estimand).

The 5 attributes of the efficacy estimand are provided in Table 1.

[figure not shown]
Table 1: Attributes of Efficacy Estimand

[figure not shown]
Estimand Attribute	Elements
Population	All subjects with PBC who participated and are actively taking investigational product in Study 747-213 or Study 747-214 (or other Sponsor studies)
Treatment	OCA+BZF FDC Tablets
Efficacy Endpoint	All efficacy endpoints
Intercurrent Events	Use of Prohibited medication (Treatment Policy) Treatment Discontinuation (Treatment Policy)
Primary Efficacy Endpoint Population Level Summary	Descriptive summary in the target population

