9.2.1.1. Child-Pugh

The Child-Pugh score (CPS) is calculated within EDC by adding the scores of the 5 factors and can range from 5-15. Child-Pugh class is either A (a score of 5-6), B (7-9), or C (10 or above). Each of the factors is outlined in Table 2.

Table 2: Child-Pugh Score

Factor	Units	Points		
		1	2	3
Serum bilirubin	μmol/L	<34	34-50	>50
	mg/dL	<2.0	2.0-3.0	>3.0
Serum albumin	g/L	>35	35-28	<28
	g/dL	>3.5	3.5-2.8	<2.8
Prothrombin time	Seconds prolonged	0-3	4-6	>6
	INR	<1.7	1.7-2.3	>2.3
Ascites		None	Mild	Moderate-Severe
Hepatic encephalopathy		No	Grade 1 or 2	Grade 3 or 4

The ascites and hepatic encephalopathy variables are based on the investigator's clinical assessment.

The CP score will be summarized in the same manner as described above for the MELD score.

Child-Pugh class will be presented in shift tables showing the shift from baseline to each scheduled post-baseline visit by the count and percentage of subjects within each shift classification.

Individual factors will be presented in a listing.

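### Permitted anticoagulants can raise INR enough to meet Table 5's MELD stop criterion or to shift Child-Pugh class, and neither Table 5 nor the visible SAP says how such values are handled

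*Protocol*

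**What the plan says.** **Anticoagulants are allowed.** Protocol 9.2.3: "Use of anticoagulants (e.g., warfarin) should be monitored and the dose adjusted, if needed". Section 5.6.2 notes that some subjects are on anticoagulants and that "BZF may enhance the action of anticoagulants of the coumarin type"; Section 9.2.8 repeats the interaction. OCA is said to lower INR slightly with warfarin, so INR may move either way.

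**The stop rule.** Protocol 7.4.3: "Investigational product is to be permanently discontinued with the development of any clinical events listed in Table 5". Under evidence of hepatic decompensation, Table 5 lists "Progression to CP score ≥7" and MELD ≥15. Section 8.4.1 repeats the rule. Neither place mentions the cause of a raised INR.

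**Guards elsewhere in the protocol.**
- Section 14.2.1 applies to MELD ≥15 as an outcome endpoint. It requires cirrhosis, progression and a sustained change, and says that "transient increases of total bilirubin, creatinine, or INR values due to causes other than progression of liver disease should be ruled out", giving INR-raising medication as the example.
- Section 7.4.4.1 lists, among the findings that count as cirrhosis when combined with low platelets, "Elevation in PT/INR (not due to antithrombotic agent use), or" further items.
- Section 7.4.4 has CP calculated in everyone but applied only to subjects meeting the cirrhosis criteria. Without cirrhosis, CP may not be the sole ground for discontinuation.

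**The SAP.** Section 9.1 lists "Change from baseline in the GLOBE, UK-PBC, and MELD scores" as an endpoint. Section 9.2.1.1 says "Child-Pugh class will be presented in shift tables showing the shift from baseline to each scheduled post-baseline visit". No rule for values taken on an anticoagulant is visible, and CP is not restricted to cirrhosis. The intercurrent events are prohibited medication and treatment discontinuation, so a permitted anticoagulant falls outside them.

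**The concern.** The protocol recognises in two places that an INR raised by a drug says nothing about the liver, but it does not attach that recognition to the Table 5 MELD item. The same laboratory value could be rejected as an outcome under Section 14.2.1 and still require permanent discontinuation, listed as evidence of hepatic decompensation, under Section 7.4.3.

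Long-term safety is the primary objective of this single-arm study. There is no comparator in which a drug-driven rise in MELD or CP would also appear and so be recognised. Entry criteria screen out decompensation, so even one or two artefactual class A-to-B shifts would be conspicuous in the tables. The SAP as visible gives the reader no way to separate them from liver worsening, apart from a listing of the individual CP factors.

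**Working it through.** The plan states no figure on this point, so there is none to reproduce. The check is whether INR alone can reach the Table 5 thresholds in a subject whose liver and kidney values are otherwise unremarkable.

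**Inputs**
- MELD (Protocol 14.2.1): 3.78 ln(bilirubin) + 11.2 ln(INR) + 9.57 ln(creatinine) + 6.43, in mg/dL. No lower bound on the inputs is stated.
- Bilirubin: entry requires ≤ULN (Protocol 8.3, criterion 3). The SAP 10.3 upper limit is 12.3 µmol/L. The protocol equates 3 mg/dL with 51.3 µmol/L, so 12.3 / 17.1 = 0.72 mg/dL.
- Creatinine: SAP 10.3 normal range 0.57–1.27 mg/dL.
- CP points: Protocol Table 6.

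**MELD.** Solving for a score of 15: INR = exp[(15 − 6.43 − 3.78 ln b − 9.57 ln c) / 11.2]. For b = 0.72 and c = 1.0: (8.57 + 1.25) / 11.2 = 0.876, and exp(0.876) = 2.40. The other rows follow in the same way.

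| Bilirubin, creatinine (mg/dL) | MELD at INR 1.0 | MELD at INR 2.5 | INR giving 15 |
|---|---|---|---|
| 0.5, 0.8 | 1.7 | 11.9 | 3.29 |
| 0.6, 0.9 | 3.5 | 13.8 | 2.79 |
| 0.72, 1.0 | 5.2 | 15.4 | 2.40 |
| 0.72, 1.27 | 7.5 | 17.7 | 1.96 |
| both set to 1.0 (assumed lower bound) | 6.4 | 16.7 | 2.15 |

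Scores are recorded as whole numbers. If 14.5 is recorded as 15, the last column becomes 3.14, 2.67, 2.30, 1.87 and 2.06. The 1.27 row is the top of the normal range, and the eGFR <60 mL/min exclusion may remove some such subjects at entry.

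The documents give no anticoagulant INR range. If one assumes 2 to 3, the threshold is crossed within that range in four of the five rows and not in the first.

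**Child-Pugh.** With bilirubin <2.0 mg/dL (1), albumin >3.5 g/dL (1), no ascites (1) and no encephalopathy (1):
- INR <1.7: 1 + 1 + 1 + 1 + 1 = 5, class A
- INR 1.7–2.3: 1 + 1 + 2 + 1 + 1 = 6, class A
- INR >2.3: 1 + 1 + 3 + 1 + 1 = 7, class B

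With albumin exactly 3.5 g/dL, which entry allows, albumin scores 2 and INR 1.7 already gives 7.

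**Effect on the tables.** A rise in INR from 1.0 to 2.5 adds 11.2 × ln 2.5 = 10.3 MELD points, whatever the other two inputs (no lower bound applied). With 133 subjects at a visit, one such subject moves the mean change by 10.3 / 133 = 0.08 points and adds 1 / 133 = 0.75% to the A-to-B cell. The mean is hardly touched. The class shift, the maximum and the individual stop are where it shows.

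**Which guard reaches which use**

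| Use of the score | Guard against drug-raised INR |
|---|---|
| MELD ≥15 as outcome endpoint | Yes (14.2.1) |
| MELD ≥15 as stop criterion | None stated |
| CP ≥7 as stop criterion, no cirrhosis | Yes, in effect (7.4.4) |
| CP ≥7 as stop criterion, compensated cirrhosis | None stated |
| SAP MELD change | None visible |
| SAP CP score and class shift | None visible |

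**The case against.** The case against has several sound parts.

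- **CP stops are largely guarded.** Section 7.4.4 prevents a stop based solely on CP in subjects without cirrhosis. That stands; the CP route is open only in compensated cirrhosis.
- **Endpoint and stop rule differ in purpose.** A sensitive stop rule beside a specific endpoint is not in itself a contradiction, and suspected liver outcomes are adjudicated. This is fair, but the protocol does not say that the difference is intended, and Table 5 presents the MELD item as evidence of decompensation.
- **The exposed group is narrow.** Exclusion criterion 3 bars INR >1.7 at entry. Those at risk are subjects who start an anticoagulant on study or whose INR rises on bezafibrate.
- **Investigators have latitude.** Section 7.4.2 allows an alternate follow-up with documented Medical Monitor agreement. It sits with the laboratory interruption criteria and is not clearly extended to Table 5.
- **SAP text may be missing.** Section 9.2.1.1 refers back to a MELD description that cannot be seen in the public copy. The absence of a rule is therefore a statement about the visible text only.
- **Removing values could hide true worsening.** This is right, and it would fit badly with the SAP's treatment-policy approach.

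A reader might infer that any anticoagulated subject with a stable liver must be stopped and will be counted as a hepatic event. The documents do not support that: the MELD threshold depends on bilirubin and creatinine, and Section 14.2.1 protects the outcome endpoint. Nor do Table 4 and exclusion criterion 3 make the point stronger. Table 4 uses INR >1.5 only together with an ALT or AST rise and allows restart, and the exclusion reduces exposure.

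**Conclusion.** The point holds in a limited form. Table 5 and Section 8.4.1 require permanent discontinuation at MELD ≥15 with no reference to a drug-raised INR, and at CP ≥7 in compensated cirrhosis likewise. INR alone can reach MELD 15 with normal bilirubin and creatinine, at 1.96 to 3.29 over the unfloored inputs shown, or at 2.15 if bilirubin and creatinine are floored at 1.0. INR above 2.3 alone produces a class A-to-B shift, which the SAP would tabulate in all subjects although Section 7.4.4 confines the use of CP to those meeting the cirrhosis criteria.

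This rests on three assumptions: that some on-study INRs reach these levels, that the formula is used as printed (or with the stated floor), and that the missing SAP text contains no rule. The number of subjects affected is not given and cannot be derived. A claim that anticoagulant users would supply most of the apparent hepatic worsening would need a usage rate that the documents do not contain.

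**What to change.** **Protocol.** Section 7.4.3 with Table 5, and Section 8.4.1, must be reconciled with Sections 7.4.4, 7.4.4.1 and 14.2.1 on a medication-related INR, so that a site can tell which instruction governs. Which clinical rule applies is for the sponsor to decide. Table 4 and exclusion criterion 3 need not change for this purpose.

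**SAP.**
1. Present the CP class shift table for subjects meeting Section 7.4.4.1, with the all-subject version as a listing or supplement.
2. Flag each MELD, CP and Mayo Risk Score value taken while the subject was on an anticoagulant that affects INR (Mayo uses prothrombin time). Protocol 9.2 already collects the data. Build the flag from recorded start and stop dates, because the concomitant-medication definition in SAP 10.7, as worded, mentions only drugs started before the first dose.
3. Keep all values in the main summaries and add a supportive summary without the flagged values.
4. State whether lower bounds apply to the MELD inputs, if the full SAP does not already do so.

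**Cost.** One derived flag, one extra table and a clarification in the next amendment. No new data are collected and no observed value is dropped from the main summaries.
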